More recently, Lanzkrom et al have published a study attempting to compare outcomes in infusion centres (IC) with ED³. The ESCAPED (Examining Sickle Cell Acute Pain in the Emergency Versus Day Hospital) study was a prospective observational study in four US cities. The investigators considered that randomly assigning to ED or IC was not possible because patients are reluctant to be assigned to ED-only care, and also because of the practical challenges of randomising during an acute VOC event. Patients would be preferentially treated in an IC during working hours, but for various reasons (low staffing, non-availability of beds, additional complications) might be allocated to care in ED. In order to account for potential bias in the type of patient and presentation being treated in IC or ED, a propensity score was applied to each event. Patients treated in an IC received parenteral pain medication substantially faster than those seen in the ED, were more likely to have their pain reassessed 30 minutes after their initial dose of parenteral medication and substantially less likely to be hospitalized than those who received care in an ED. A subsequent health economic analysis of this study suggested large savings in medical and societal costs in the US, largely driven by reduction in hospital admissions in those attending IC.¹¹

One potential concern is whether opening an acute care facility might encourage patients to attend hospital for pain control rather than managing their pain at home, and this could increase hospital admissions and chronic opioid exposure. This might need to be managed by restricting access to facilities for high frequency service users. It is also not clear how the facility would be made available to patients in low-prevalence areas, with more limited specialist service provision. One proposed solution is provision of a centralised Hyper-acute Unit providing acute care for all service users in the region, and open 24 hours a day.¹² This type of unit may be suitable for service users who are local to the unit, but might entail prolonged travel for those living in other parts of the region, and might substantially increase the volume of patients requiring care and potentially hospital admission, in the hospital where the unit is hosted.

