6.4 Secondary endpoints

- Time to first analgesia, defined as time from presentation in ACU or ED to first dose of opioid analgesia administered. (For subjects given parenteral opioid prior to arrival in care unit, e.g. in ambulance, timing will start from one hour after parenteral analgesia given in ambulance, even if subject presents less than one hour after analgesia given in ambulance)
- Adherence to NICE guideline in safety observations (defined as proportion of hourly safety observations (respiratory rate, sedation score) taken within first 6 hours (+/- 30 mins)
- Adherence to care plan in analgesia doses (defined as proportion of analgesia doses given according to protocol within first 6 hours (+/- 30 minutes)
- Fit for discharge by 6 hours after first analgesia (defined as pain score 5 or less for at least 2 consecutive hourly assessments; no requirement for parenteral opioid for at least 2 hours and acceptable oral analgesia protocol available for use at home, NEWS score green for >2 hours, patient able to self-administer oral medication, patient mobile. All the above assessed by physician and agreed with patient)
- Time from first analgesia to fit for discharge (defined as pain score 5 or less for at least 2 consecutive assessments; no requirement for parenteral opioid for at least 2 hours and acceptable oral analgesia protocol available for use at home, NEWS score green for >2 hours, patient able to self-administer oral medication, patient mobile. All the above assessed by physician and patient).
- Cumulative dose of morphine or equivalent opioids in first 6 hours and first 24 hours
- Proportion admitted to hospital from ACU or ED
- Length of hospital stay (for those admitted to hospital), length of hospital stay Patient satisfaction with care assessed using SCAPE questionnaire 14 and 28 days after discharge
- Health economic analyses of comparative patient health-related quality of life, costs and cost-effectiveness of ACU versus ED care from the perspective/s of health and social care (NHS and PSS) and, separately, wider society
 - Costs at 28 days post-randomisation
 - QALY at 28 days post-randomisation
 - Incremental cost-effectiveness ratio

7. Study population

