Patients will not be randomised if:

1. Pain can be managed without the need for hospital attendance.

2. Symptoms suggest a complicated crisis, where additional medical problems need to be managed.

3. ACU is not available at the trial centre.

The procedure for these different eventualities is illustrated in the flow-chart (Appendix 3).

Randomised patients

For randomised patients, their management will be implemented by their health care team for ED or ACU, using their pre-agreed pain management protocol. The trial team will not be responsible for treating the patient, but will have the following responsibilities:

- Confirmation of consent, eligibility and allocation to correct treatment location
- Pain score (0-10 numeric rating scale) at baseline and hourly for first 6 hours
- Collection of the following data:
 - a) Safety data (respiratory rate and sedation score) hourly for first 6 hours (taken from hospital paper or electronic record. Record actual values and percentage of scheduled measurements.
 - b) Adherence to pre-agreed pain management protocol.
 - c) Cumulative opioid dose over the first six hours (from hospital paper drug chart or electronic prescribing record) and duration of episode in ED or ACU (APC episode resource use CRF).
 - d) Whether the patient is admitted or discharged from ED or ACU.
 - e) Any additional analgesic medication and all non-analgesic medication.
 - f) Health economic data (Section 11.3)

- g) Patient satisfaction questionnaire, taken 14 and 28 days after presentation using the SCAPE questionnaire.
- h) Quality of life assessment; using the EQ-5D-5L tool taken on consent, presentation, 6 hours, 14 and 28 days after the presentation.
- i) Length of stay for patients admitted to hospital. Defined as time from the decision to admit, to time patient leaves ward.
- j) Re-attendance rate (within 7 days).
- k) Complication rate (acute chest syndrome, other acute sickle complications, physician diagnosis from discharge summary).
- I) Education/employment/daily activity loss (social determinants of health assessment).
- m) Resource use CRF including Work Productivity and Activity Impairment Questionnaire, collected at consent, 14 days and 28 days follow-up.

Observational Arm

Consented subject may be triaged with an uncomplicated APC, but cannot be randomised for a number of reasons including:

- No trial staff available
- No available space on ACU
- ACU is closed
- Presenting within 6 hours of closure of ACU

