11.1 Sample size

The target sample size is 228 patient episodes (114 per group). This provides 90% power (with 2-sided α =0.05) to detect a mean difference between ambulatory care and hospital emergency department of 1.3 in pain scores on a 0-10 visual analogue scale at 6 hours after presentation. A difference of 1.3 in pain scores has been used as a clinically important difference in other studies.^{9, 19} Data from the SCAPE trial provided an estimate of 3.2 for the standard deviation (SD) for pain scores and informed a conservative estimate of the correlation between baseline and 6-hour pain scores of 0.5¹⁸. The sample size allows for a conservative 15% dropout by 6 hours, informed by data from the SCAPE trial. It is anticipated that dropout will be minimised by potential use of an app to collect data including pain scores.

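### Both fit-for-discharge endpoints run from first analgesia, while the primary endpoint, hourly scores and ACU opening rule run from presentation: waiting time drops out of them and the 6-hour point overruns the hourly grid

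*Protocol*

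**What the plan says.** Protocol 6.4 has two endpoints on fitness for discharge. The binary one is "Fit for discharge by 6 hours after first analgesia (defined as pain score 5 or less for at least 2 consecutive hourly assessments", followed by further criteria (parenteral opioid need, NEWS, oral medication, mobility). The other is "Time from first analgesia to fit for discharge", with nearly the same criteria, except that its two consecutive assessments are not said to be hourly. The same list carries the delay as an endpoint of its own: "Time to first analgesia, defined as time from presentation in ACU or ED to first dose of opioid analgesia administered".

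The other 6-hour clocks start at presentation:

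- 6.3: the primary endpoint.
- 11.1: the trial is sized on a difference "of 1.3 in pain scores on a 0-10 visual analogue scale at 6 hours after presentation".
- 11.2: the model uses baseline and each hour to 6 hours from presentation.
- 7.2: an episode is excluded if the ACU has less than 6 hours of opening left at presentation.

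Section 8 asks for "Pain score (0-10 numeric rating scale) at baseline and hourly for first 6 hours", and the pain-score footnote in 9.6 agrees. The schedule in 9.6 also marks a pain score at discharge, at 14 days and at 28 days, and has a row for time to readiness for discharge. Section 14.2 lists a clinical assessment form for 6 to 24 hours without describing its content. Under 9.4, randomisation is done by phone before the patient arrives.

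**The concern.** The trial compares two care pathways, and time to treatment is part of what distinguishes them. Section 5.1 names delays in triage and assessment among the problems of ED care, and reports of an observational study in the United States that "Patients treated in an IC received parenteral pain medication substantially faster than those seen in the ED". An endpoint whose clock starts at the first dose begins after that part of the pathway is over. The starting point is then set by care given after allocation and need not be comparable between arms.

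There is also a mismatch of grids. The binary endpoint needs two consecutive hourly scores in a window that starts at the first dose, but the hourly scores are laid out from arrival. The later the first dose, the more of the window lies beyond the last hourly score. What is at stake is how these two secondary endpoints can be read, not the primary analysis.

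**Working it through.** **The plan's own figure.** No number is given for the fit-for-discharge endpoints. The only stated size is 228 episodes (114 per group) for the primary outcome, from a difference of 1.3, SD 3.2, correlation 0.5, 90% power, two-sided 0.05 and 15% dropout (all in 11.1). It reproduces:

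- Adjusted SD = 3.2 × √(1 − 0.5²) = 2.771.
- n per group = 2 × [2.771 × (1.960 + 1.282) / 1.3]² = 95.5, so 96. With the t distribution it is 97.
- 97 / 0.85 = 114.1 per group, in line with the stated 114.

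Nothing below changes it.

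**Grid check.** Hourly scores fall at 0, 1, …, 6 h after presentation. With the first dose at D hours, the endpoint window runs from D to D + 6. The next table counts the whole hours in that window, and those that have a scheduled score.

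| D (h) | 6-hour point, h after presentation | Whole hours in window | Scheduled hourly scores | Consecutive pairs available |
|---|---|---|---|---|
| 0.5 | 6.5 | 6 | 6 | 5 |
| 1 | 7 | 7 | 6 | 5 |
| 1.5 | 7.5 | 6 | 5 | 4 |
| 2 | 8 | 7 | 5 | 4 |
| 3 | 9 | 7 | 4 | 3 |

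The last D hours of the window have no scheduled hourly score. For a patient who arrives at the limit allowed by 7.2, the 6-hour point can also fall D hours after the ACU has closed.

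**Clock check (illustration).** The documents give no delay in minutes and no distribution of time to fitness, so these are assumptions: time T from first dose to fitness has the same distribution in both arms; first dose at 0.5 h in ACU and at 1, 1.5 or 2 h in ED. Then

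- fit by 6 h after first analgesia = P(T ≤ 6), the same in both arms whatever the delays;
- fit by 6 h after presentation = P(T ≤ 6 − D).

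| Distribution of T | Stated clock, both arms | From presentation: ACU | ED, D = 1 / 1.5 / 2 h | Difference (points) |
|---|---|---|---|---|
| Gamma, shape 4, mean 6 h | 56.7% | 49.9% | 42.7 / 35.3 / 27.9% | 7.2 / 14.6 / 22.0 |
| Lognormal, σ 0.6, median 4 h | 75.0% | 70.2% | 64.5 / 57.8 / 50.0% | 5.7 / 12.4 / 20.2 |
| Lognormal, σ 0.6, median 5 h | 61.9% | 56.3% | 50.0 / 43.0 / 35.5% | 6.3 / 13.3 / 20.8 |
| Lognormal, σ 0.6, median 8 h | 31.6% | 26.6% | 21.7 / 16.9 / 12.4% | 4.9 / 9.7 / 14.2 |

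The range is about 5 to 22 points. For the time-to-event endpoint, median time from presentation differs by the delay difference, 0.5 to 1.5 h; from first analgesia it does not differ.

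**The two effects together.** The figures for the stated clock assume that fitness is seen whenever it occurs. If nothing after hour 6 were usable and such episodes counted as not fit, the stated endpoint would reduce to P(T ≤ 6 − D), the presentation result (apart from rounding to whole hours). With full later ascertainment it shows no difference. Excluding unobserved episodes could give something else again. So the first effect favours the slower arm, the second counts against it, and the protocol does not fix the balance.

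**The case against.** The strongest reply is that the bullets split the pathway on purpose: presentation to first dose is one endpoint and first dose to fitness another, so the delay is reported separately. That is right as far as it goes. A reader might infer that slow ED treatment is erased from the trial; it is not, because time to first analgesia measures it and the primary outcome runs from presentation. The point is confined to these two endpoints.

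A reader might also infer that the 6-hour point always falls after all scheduled pain scoring. The documents do not support that. A discharge score and a 6 to 24 hour assessment are listed, and fitness is a joint judgement by physician and patient, not a reading of trial pain scores alone. Section 6.4 also provides for opioid given in the ambulance without saying whether that dose starts this clock; if it does, a dose 0.5 h before arrival puts the 6-hour point at 5.5 h, inside the grid. What stands is narrower: hourly scoring ends at 6 hours, and no later hourly series is specified.

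A longer ED delay is expected, not shown. The evidence is observational and from the United States, section 5.2 cautions that such results may not carry over to the NHS, and section 10 says both arms include measures to improve on current care. The equal response in the illustration guarantees a null result on the stated clock.

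Finally, presentation also follows phone randomisation, so it is not a perfect origin. But it is the origin the protocol uses for its primary endpoint, and it precedes the hospital care being compared. Episodes with no opioid would have no time zero, which fits poorly with the intention-to-treat statement in 11.2; given the entry criteria these may be few, and the point adds little weight.

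**Conclusion.** The concern holds for two secondary endpoints. Their time origin is a post-randomisation event that the pathway is expected to move, and it does not match the presentation clock used for the primary endpoint, the hourly grid and the ACU opening rule. Followed as written, both leave waiting before the first dose out of a pathway comparison, and the binary one looks for hourly scores in a stretch of D hours where none is scheduled.

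On size, delays of 1, 2 and 3 h leave 1, 2 and 3 whole hours of the window unscored; that is arithmetic on the protocol's own grid. The 5 to 22 percentage points are illustrative, rest wholly on the assumed delays and distributions, and should not be read as a forecast or as a real effect that the trial would lose. I assign no net direction of bias. The primary analysis and the sample size are untouched. The time origin is written into the protocol's endpoint definitions, so it should be changed there and not left for a later plan to replace. The clinical criteria for fitness are not judged here.

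**What to change.** In 6.4, redefine the two endpoints as *fit for discharge by 6 hours after presentation* and *time from presentation to fit for discharge*. Keep the versions from first analgesia as supportive, and say whether a dose given before arrival starts that clock. Use the same wording, two consecutive hourly assessments, in both bullets.

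The binary endpoint then fits the existing 0 to 6 hour grid with no extra scoring. Re-timing does not by itself cover the time-to-event endpoint after hour 6. For that, take the time of fitness from the readiness-for-discharge record (9.6) and the 6 to 24 hour assessment (14.2). Do not censor at the last hourly pain score: patients not yet fit at hour 6 are likely to be those doing worse, so that censoring would be informative.

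The cost is a wording change in 6.4 that uses times already recorded, plus a check that the two later records hold a clock time for fitness, since the protocol does not describe their content. The sample size does not change. The downside is that the re-timed endpoints no longer isolate response after treatment; the supportive versions retain that.

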Potential alternatives to current ED care include specialised units providing care in an alternative hospital-based setting. These are variously described as ambulatory units, day care units or infusion centres. For the purposes of this study we refer to them as Specialist Hospital-based Ambulatory Care Units (ACUs). The ASH guideline specified that patients on these units should be managed by a team specialised in acute SCD pain management, and should be located in a hospital with easy access to acute and intensive care facilities, recognising that occasionally patients present with acute pain together with life-threatening complications including acute chest syndrome and sepsis. This type of care provision is generally available during working hours only (Monday to Friday, 9am to 5 pm), although there are some examples of extended opening hours.^{3, 4}. The unit could be entirely dedicated to SCD, or alternatively, with smaller patient populations or insufficient dedicated staff and space, the service could be embedded in a larger multi-specialty unit, such as a hospital-based haemato-oncology unit.^{3, 5}

Currently, there are no randomised studies comparing standard ED care with ACU's, and relatively few observational studies, which are predominantly from a United States health care perspective. Reports in the 1990's from Montefiore Medical Centre, New York, USA⁶, and the Day Centre at Birmingham City Hospital, UK⁷, demonstrated satisfactory pain control, and reduction in hospital admissions, leading to significant cost savings for the service. These finding have subsequently been replicated in other centres such as an infusion clinic at Johns Hopkins Medical Centre and in the paediatric setting^{3, 4, 8, 9}. A report from a day care unit in Jamaica where the unit was not located in a hospital setting highlighted the potential for harm. Fatal events were reported in a small number of patients who had been discharged home, with causes of death including acute chest syndrome and sepsis.¹⁰

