5.2 Rationale

The aim of this study is to build on current evidence summarised above, by conducting a trial to make a direct comparison of two care pathways currently available in the NHS for hospital management of acute sickle pain to establish the clinical and cost-effectiveness of an ambulatory care unit in comparison with current emergency department care in NHS institutions.

Current emergency department care often fails to meet national standards, and patient experience is often poor with significant variation in care across the NHS. An improved care pathway is needed, and there is data from retrospective and prospective nonrandomised studies indicating better outcomes with ambulatory care units compared to current ED care. These have largely been from the USA health care perspective and results may not be directly applicable to the NHS in England. There has never been a randomised study comparing ED and ambulatory care, and the need for well conducted randomised studies in this area have been highlighted in both the NICE and ASH guidelines on sickle pain management.

Although it seems likely that ambulatory care would be preferred by patients, it is not clear how much difference may be achieved in clinical outcomes of value to the patient, such as reduction in pain, in patient-reported quality of life, and in health care metrics, such as probability of being admitted to hospital rather than discharged home, and bed days spent in hospital for those admitted. These metrics would inform whether investing in setting up ambulatory care represents improved patient-centred outcome.

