The All Party Parliamentary Group on Sickle Cell Disease and Thalassaemia report 'No One's Listening' summarised experiences and opinions from health care professionals, patients and families concerning deficiencies in NHS care for acute sickle pain. One recommendation of this report was to commission work on clinical trial design to address deficiencies in evidence of effective interventions. The NHS Race and Health Observatory, an independent organization, set up to explore ethnic inequalities in healthcare and to provide recommendations to inform policymaking and facilitate change, subsequently invited applications for a grant to develop a clinical trial addressing these deficiencies. This tender was awarded to the group developing the current protocol. The core of this group consisted of members of the National Sickle Pain Group, which had been supported by the NHS England Clinical Reference Group for specialised commissioning of haemoglobin disorders, and included a range of health care professionals and patient representatives. The patient representative for this project was delegated by the Sickle Cell Society and was involved in all stages of protocol development.

The protocol development included a national workshop held in May 2023, during which relevant literature was reviewed, care models in the USA were presented, and potential trial designs were discussed. The workshop was attended by health care professionals, health service managers and commissioners, patients, carers and representatives of the Sickle Cell Society.

By undertaking the current study, emergency department and haemoglobinopathy services in NHS institutions will become more engaged in quality improvement regarding acute pain management in sickle cell disease. The study will foster a more uniform approach to acute pain management across the NHS. The proposal to study the implementation of individual pain protocols by dedicated staff in two different acute settings will help to embed two vital elements of care (individual protocols and dedicated sickle pain specialist nurses) into routine care.

In addition, the trial will answer important questions for quality of care and the costeffectiveness of ambulatory care units such as:

-Can hospital admissions be avoided?

-Can existing NHS quality standards around acute sickle pain management be better achieved?

-Can patient quality of life and satisfaction be improved?

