11.2 Method of analysis

Baseline characteristics will be summarised for each randomised group using descriptive statistics.

Pain scores at each time-point will be described for each randomised group using mean (SD), or median (interquartile range, IQR) if distributions are skewed. The primary outcome of pain score over the 6 hours following presentation will be compared between randomised groups using a longitudinal mixed linear regression model that includes all timepoints from baseline, and at each hour up to 6 hours after presentation. Performing a longitudinal analysis of all time-points using all non-missing data should allow for greater precision in the estimation of treatment effect specifically at 6 hours (the primary outcome) than an analysis of this time-point alone. The model will include fixed effects for intervention (ACU versus ED) and for the stratification factors age and previous history of acute pain crises, with random effects for site, timepoint and APC. The treatment effect of ACU versus ED will be summarised by an adjusted mean difference in pain scores with a 95% confidence interval, and significance assessed using the Wald test.

The mixed-effects model assumes that data are missing at random, i.e. results are unbiased if missingness is related to observed outcome data or stratification factors from the same participant. Patterns of missingness in the primary outcome data will be examined and a sensitivity analysis will estimate the treatment effect with missing data imputed.

The unit of randomisation is an APC, and participants may be randomised more than once within the trial. Previous studies have not shown evidence of clustering within participants in terms of outcomes for separate episodes¹⁸, but this will be tested for in a sensitivity analysis for the primary outcome by including a random effect for participant in the regression model.

Secondary outcomes will be compared between randomised groups using methods appropriate for the type of data.

Analyses will be done on an intention-to-treat basis, including all participants according to randomised allocation.

Data collected from participants in the observational cohort will be summarised separately from those randomised into the trial using descriptive statistics.

Full details of analyses will be described in a separate Statistical Analysis Plan.

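### Length of stay is compared only among admitted patients, although ACU care is expected to change who is admitted; bed-days per randomised episode would keep the comparison randomised

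*Protocol*

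**What the plan says.** Section 6.4 makes "Length of hospital stay (for those admitted to hospital" a secondary endpoint. Section 8, under randomised patients, gives the definition: "Length of stay for patients admitted to hospital. Defined as time from the decision to admit, to time patient leaves ward". A patient sent home from the unit has no decision to admit and so has no value. Section 5.2 words the bed-use metric in the same conditional way: "bed days spent in hospital for those admitted".

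Admission is a separate secondary endpoint in Section 6.4: "Proportion admitted to hospital from ACU or ED". The protocol expects ACU care to affect it:
- Section 5.1 cites early day-unit reports of "reduction in hospital admissions, leading to significant cost savings for the service".
- Section 5.1 also cites a prospective cohort whose infusion-centre patients were "substantially less likely to be hospitalized than those who received care in an ED".
- Section 5.2 asks "Can hospital admissions be avoided" as a question for the trial.

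On the analysis population, Section 11.2 states: "Analyses will be done on an intention-to-treat basis, including all participants according to randomised allocation". It also says that secondary outcomes will be compared between the randomised groups.

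**The concern.** The endpoint selects patients on an event that happens after randomisation and that the intervention is meant to influence. If ACU care avoids some admissions, the admitted ACU patients are the ED-type admissions minus those avoided. Any difference in mean stay then mixes a real effect on stay with a change in who is counted, and randomisation cannot separate the two.

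The SAP may choose the statistical method, but the protocol has already fixed the population. That population also cannot be squared with an intention-to-treat analysis of all participants.

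At stake is how this endpoint is read. Section 5.2 puts bed days among the measures that would inform investment in ACUs, yet no listed endpoint clearly counts bed-days over all randomised episodes.

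**Working it through.** The protocol states no admission rate and no length of stay, so there is no figure to reproduce on this point. The only input taken from it is the 114 episodes per group in Section 11.1. Everything else below is an assumption, varied over a range.

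**Model.** Divide episodes into those admitted under either arm (stay L), those admitted under ED but not under ACU (stay S), and those never admitted. Let pE and pA be the proportions admitted from ED and ACU. Assume that ACU admits nobody whom ED would have sent home, and does not alter stay in those admitted either way.

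- Mean stay among the admitted, ED: [pA·L + (pE − pA)·S] / pE
- Mean stay among the admitted, ACU: L
- Admitted-only difference, ACU minus ED: (pE − pA)(L − S) / pE
- Bed-days per randomised episode, ED: pA·L + (pE − pA)·S
- Bed-days per randomised episode, ACU: pA·L
- Per-episode difference, ACU minus ED: −(pE − pA)·S

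When ACU avoids any admissions, the per-episode difference always favours ACU. The admitted-only difference goes against ACU if S < L, is zero if S = L, and favours ACU if S > L.

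**Worked case** (pE = 0.50, pA = 0.30, L = 5 days, S = 2 days).
- Admitted only, ED: (0.30×5 + 0.20×2)/0.50 = 1.9/0.50 = 3.8 days. ACU: 5.0 days. Difference +1.2 days.
- Per randomised episode, ED: 1.9 days. ACU: 0.30×5 = 1.5 days. Difference −0.4 days.
- Over 114 episodes per group: 114×1.9 = 217 bed-days against 114×1.5 = 171.

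**Range** (L = 5 days). Each cell gives the admitted-only difference, then the per-episode difference, in days (ACU minus ED).

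| Admitted ED / ACU | S = 1 | S = 2 | S = 3 | S = 5 |
|---|---|---|---|---|
| 50% / 40% | +0.80, −0.10 | +0.60, −0.20 | +0.40, −0.30 | 0, −0.50 |
| 50% / 30% | +1.60, −0.20 | +1.20, −0.40 | +0.80, −0.60 | 0, −1.00 |
| 40% / 20% | +2.00, −0.20 | +1.50, −0.40 | +1.00, −0.60 | 0, −1.00 |
| 60% / 50% | +0.67, −0.10 | +0.50, −0.20 | +0.33, −0.30 | 0, −0.50 |

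The last column is the case without selection: the endpoint shows nothing while 0.5 to 1.0 days per episode are saved.

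**Adding a real benefit.** In the worked case, let ACU also shorten stay by 0.5 days in those still admitted. The admitted-only means are 3.8 (ED) and 4.5 (ACU), so ACU still looks 0.7 days worse. Per episode they are 1.9 and 0.30×4.5 = 1.35.

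**The case against.** The strongest reply is that bed use does not rest on this line alone. The proportion admitted is listed directly above it and covers every randomised episode. Multiplying it by mean stay among the admitted recovers bed-days per episode. Costs at 28 days also cover all randomised episodes, and Section 11.3.2 includes the index unit episode, any resulting admission and linked hospital records. Cost-effectiveness, unlike stay, is a stated secondary objective. Most of this stands, and it limits the harm to the stay endpoint read by itself.

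It does not remove the defect. The product is not a planned endpoint with its own confidence interval, and it fails if stay is summarised by a median. The costing applies a unit cost to longer admissions, so it registers an avoided admission better than it registers bed-days.

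Two stronger readings are tempting:
- A reader might infer that the endpoint will show ACU to be worse while bed use falls. The documents do not support that. It requires avoided admissions to be shorter than the rest, which is plausible but nowhere stated, and any real ACU effect on stay would also move the result.
- A reader might infer that, because the clock starts at the decision to admit, time in the unit is lost to the trial. It is not. Section 8 item (c) collects the duration of the ED or ACU episode, and Section 11.3.2 uses it in costing.

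Finally, the same bullet in Section 6.4 mentions stay a second time without the admitted-only qualifier, run into the satisfaction endpoint. It may be an editing remnant or a garbled all-patient measure. Section 8 supplies only the admitted-only definition, so an all-patient version, if intended, is undefined.

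**Conclusion.** The point holds for this one secondary endpoint. That the admitted-only comparison is not protected by randomisation, and conflicts with the intention-to-treat statement in Section 11.2, follows from the text together with the protocol's own expectation that ACU reduces admission. It needs no numerical assumption.

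The direction and size of any distortion are not established. Under the assumed rates and stays, the endpoint read alone ranges from no difference, hiding a saving of 0.5 to 1.0 bed-days per episode, to ACU appearing 0.33 to 2.0 days worse while saving 0.1 to 0.6. These ranges describe the chosen scenarios and do not forecast the result. The primary endpoint and the sample size are unaffected. The change is worth making because it is cheap and the measure is meant to inform investment.

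**What to change.** In Sections 6.4 and 8, make the compared endpoint hospital bed-days per randomised episode, with 0 for patients not admitted. State whether it covers the index admission only or runs to 28 days using the linked records already planned in Section 11.3.2. Analyse it with a method suited to skewed data with many zeros, such as a bootstrap interval for the difference in means.

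Report length of stay among the admitted descriptively, beside the proportion admitted. Align the bed-day wording in Section 5.2. In Section 6.4, delete or define the second, unqualified mention of stay and separate it from the satisfaction endpoint.

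The cost is wording and a little more analysis. For the index admission, disposition and stay are already collected under Section 8, so no new data item is needed. The drawback is a skewed, zero-heavy outcome.
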